It is the responsibility of the PI and the research team to ensure serious adverse events are reported according to the Code of Federal Regulations, Good Clinical Practices, the protocol guidelines, the MDACC IND office guidelines, and Institutional Review Board policy.

11.4.3 Investigator Communication with Supporting Companies

To protect human subjects, entities that provide the IMGN901 drug to or receive the IMGN901 drug from other entities will share safety information with each other. To that end, the PI and the research team will provide copies of IND Safety Reports within 24 hours of submission to ImmunoGen, Inc. Pharmacovigilance and, upon request, the Safety Officer of other IMGN901 entities. In turn, the MD Anderson IND office (or study Principal Investigator) will receive IND Safety Reports originating from other entities using IMGN901. Each entity will provide notification when their study is closed and no further safety data will be forthcoming

12 STATISTICAL CONSIDERATIONS

The primary objectives of the study are to evaluate the overall response rate to IMGN901 in patients with CD56 expressing hematological malignancies including but not limited to relapsed/refractory leukemia, myelofibrosis refractory to ruxolitinib or JAK-inhibitor therapy, and BPDCN. A response and toxicity summary for each treatment cohort (1, 2 and 3) will be submitted to the IND Medical Monitor per the guidelines found in the statistical section 12.0.

Cohort 1 (Relapsed/refractory leukemia)

The primary objective of cohort 1 is to assess the efficacy of treatment of IMGN901 in CD56 expressing hematological malignancies including but not limited to AML, high-risk MDS, natural-killer leukemia, acute lymphoblastic leukemia, accelerated and blast-phase CML who have failed prior therapy or for which no standard therapy exists. We anticipate that the majority of the patients in this cohort will be relapsed/refractory AML. The efficacy of IMGN901 will be measured by the ORR, defined as CR (complete remission) + CRp (complete remission with incomplete platelet recovery) + CRi (complete remission with incomplete count recovery) within 3 cycles of therapy with IMGN901 in patients with CD56 expressing leukemia's (defined in section 10.0) who have failed prior therapy or for which no standard therapy exists.

We anticipate that the majority of patients in this cohort will be relapsed/refractory AML. The historical data suggested the ORR to current standard salvage treatment is 30%. The target ORR with the experimental treatment is 50%. The regimen of the IMGN901 will be considered worthy of

further investigation if it elicits an increase in ORR to 50% with acceptable toxicity. A >30% therapy related non-hematological grade 3/4 toxicity rate is considered unacceptable. Thus, interim monitoring rules, assuming the prior distributions above, were constructed that meet the following two conditions,

- 1) Stop if $\text{Prob}[p(\text{ORR}, E) > 0.50 | \text{data}] < 0.05$, or
- 2) Stop if $\text{Prob}[p(\text{TOX}, E) > 0.30 | \text{data}] > 0.95$,

where $P(\text{ORR}, E)$ and $P(\text{TOX}, E)$ are the true ORR and toxicity rates for the IMGN901. The first rule provides for stopping the study if the data suggest that it is unlikely (i.e., probability < 5%) that ORR rate of the IMGN901 is greater than the ORR rate of standard treatment by 20%. The second condition will stop the study early if excessive therapy-related non-hematological grade 3/4 toxicity (>30%) is highly probable (i.e., probability >95%) for the IMGN901. Monitoring for toxicity and futility will not begin until 5 patients have been evaluated, and cohort size for future evaluations is 5.

The monitoring rule for the toxicity rate, based on these assumptions and monitoring conditions above is found in Table 4. For example, accrual will cease if 4 or more patients experience toxicities among the first 5 patients.

Table 4. Stop accrual if the number of drug-related non-hematological grade 3/4 toxicities is greater than or equal to indicated (i.e., # patients with toxicities) among the number of patients evaluated				
# patients evaluated	5	10	15	20
# patients with toxicities	4-5	6-10	8-15	Always stop with this many patients

Monitoring the ORR rate, based on the above assumptions and monitoring conditions is found in Table 5. For example, accrual will cease if less than 1 patient experience an overall response within 3 cycles of IMGN901 in the first 15 patients treated. If <1/15 of the initially treated patients achieve response we will consider alternate dosing schedule with IMGN901 administered on days 1,8,15 of a 21-day cycle. This will be done in discussion with the MDACC IND office, FDA and the IRB. Rules for dose-interruption and dose-adjustment will remain as defined in the protocol.

Table 5. Stop accrual if the number with overall response is less than or equal to indicated (i.e., # patients with overall response) among the number of patients evaluated				
# patients evaluated	5	10	15	20
# patients with overall response	0	0-2	0-4	Always stop with this many patients

where $P(\text{ORR}, E)$ is the overall response rate (ORR) for the treatment. That is, if at any time during the study we determine that there is a less than 2.5% chance that ORR rate of the IMGN901 is greater than the ORR rate of standard treatment by 15% we will stop enrollment to this cohort. $P(\text{ORR}, E)$ is assumed to follow a prior of Beta (0.4, 1.6). The stopping boundaries for ORR, based on these assumptions and monitoring conditions are found in Table 7. We will apply these stopping boundaries continuously starting from the first patient in cohorts of 10. For example, accrual will cease if 0 patients experiences overall response among the first 10 patients treated within 3 cycles of therapy with IMGN901. The operating characteristics are summarized in Table 8.

Table 7. Stopping boundaries for ORR

Number of patients evaluated for overall response	10	20
Number of patients with overall response (i.e., CR, CRp or CRi) is less than or equal to	0 – 1	2-4

Table 8. Operating characteristics for monitoring ORR

True overall Response Rate	Early Stopping Probability	Average number of patients treated
0.20	0.3758	16
0.25	0.2440	18
0.30	0.1493	19
0.35	0.0860	19
0.40	0.0464	20
0.45	0.0233	20

Toxicity Monitoring

In addition, we will monitor toxicities. The probability of toxicity is denoted by $P(TOX, E)$. We assume $P(TOX, E) \sim \text{beta}(0.6, 1.4)$. Our stopping rule is given by the following probability statement: $\Pr(P(TOX, E) > 0.30 | \text{data}) > 0.85$. That is, we will stop the study if, at any time during the study, we determine that there is more than 90% chance that the toxicity is more than 30%. The stopping boundaries for toxicities, based on these assumptions and monitoring conditions is found in Table 9. We will apply the toxicity monitoring rule in cohort size of 5, starting from the 1st patient. For example, accrual will cease if all 3 patients experience toxicities among the first 5 patients treated. The operating characteristics are summarized in Table 10.

Table 9. Stopping boundaries for toxicity monitoring

The number of patients evaluated for toxicities	5	10	15	20
The number of patients with toxicities is greater than or equal to	3	5	7	9

Table 10. Operating characteristics for toxicity monitoring

True overall Toxicity Rate	Early Stopping Probability	Average number of patients treated
0.10	0.0089	20
0.20	0.0787	19
0.30	0.2607	17
0.40	0.5173	14
0.50	0.7846	10

Cohort 3 (BPDCN)

The primary objective of the cohort 3 is to assess the efficacy of IMGN901 in patients with a confirmed pathological diagnosis of BPDCN. The efficacy of IMGN901 will be measured by the ORR, defined as CR (complete remission) + CRp (complete remission with incomplete platelet recovery) + CRI (complete remission with incomplete count recovery) (as specified in section 10.0) within 3 cycles of therapy with IMGN901.

Futility Monitoring

Historical data on similar patients show a ORR of 20%. The target response rate is 35%. Given this, we will stop enrollment into this cohort if the observed patients' data suggest that:

$$\Pr(p(TOX, E) > 0.35 | \text{data}) < 0.025$$

where $p(\text{ORR}, E)$ is the overall response rate (ORR) for the treatment. That is, if at any time during the study we determine that there is a less than 2.5% chance that ORR rate of the IMGN901 is greater than the ORR rate of standard treatment by 15% we will stop enrollment to this cohort. $P(\text{ORR}, E)$ is assumed to follow a prior of Beta (0.4, 1.6). The stopping boundaries for ORR, based on these assumptions and monitoring conditions are found in Table 11. We will apply these stopping boundaries continuously starting from the first patient and in cohorts of 10. For example, accrual will cease if less than 1 patients experiences overall response among the first 10 patients treated within 3 cycles of therapy with IMGN901. The operating characteristics are summarized in Table 12.

Table 11. Stopping boundaries for ORR

Number of patients evaluated for overall response	10	20
Number of patients with overall response (i.e., CR, CRp or CRI) is less than or equal to	0-1	2-4

Table 12. Operating characteristics for monitoring ORR

True overall Response Rate	Early Stopping Probability	Average number of patients treated
0.20	0.3758	16
0.25	0.2440	18
0.30	0.1493	19
0.35	0.0860	19
0.40	0.0464	20
0.45	0.0233	20

Toxicity Monitoring

In addition, we will monitor toxicities. The probability of toxicity is denoted by $P(\text{TOX}, E)$. We assume $P(\text{TOX}, E) \sim \text{beta}(0.6, 1.4)$. Our stopping rule is given by the following probability statement: $\Pr(P(\text{TOX}, E) > 0.30 | \text{data}) > 0.85$. That is, we will stop the study if, at any time during the study, we determine that there is more than 90% chance that the toxicity is more than 30%. The stopping boundaries for toxicities, based on these assumptions and monitoring conditions is found in Table 13. We will apply the toxicity monitoring rule in cohort size of 5, starting from the 1st patient. For example, accrual will cease if all 3 patients experience toxicities among the first 5 patients treated. The operating characteristics are summarized in Table 14.

Table 13. Stopping boundaries for toxicity monitoring

The number of patients evaluated for toxicities	5	10	15	20
The number of patients with toxicities is greater than or equal to	3	5	7	9

Table 14. Operating characteristics for toxicity monitoring

True overall Toxicity Rate	Early Stopping Probability	Average number of patients treated
0.10	0.0089	20
0.20	0.0787	19
0.30	0.2607	17
0.40	0.5173	14
0.50	0.7846	10

Statistical Analysis Plan

All patients who received any dose of the study agent will be included in the analysis for efficacy and safety. Demographic/clinical characteristics (including duration of response) and safety data of the patients will be summarized using descriptive statistics such as mean, standard deviation, median and range. For the primary efficacy analysis, we will estimate the ORR for the IMGN901, along with the 95% confidence interval. Patients who drop out of the study before completing all the cycles will be treated as “failures” for the primary analysis. Overall response rate (ORR) during the study period will also be presented with the 95% confidence interval. The association between ORR and patient’s clinical characteristics will be examined by Wilcoxon’s rank sum test or Fisher’s exact test, as appropriate. Toxicity type, severity and attribution will be summarized for each patient using frequency tables. The distribution of time-to-event endpoints including duration of response, overall survival and progression free survival will be estimated using the method of Kaplan and Meier. Comparisons of time-to-event endpoints by important subgroups will be made using the log-rank tests. Correlation analysis (such as logistic regression analysis) will be conducted to determine the relationship between IMGN901 and other gene expression and clinical response.

13.0 REFERENCES:

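### Cohorts 2 and 3: the toxicity stopping rule is 0.85 in the formula but 90% in words, and the two give different boundaries at 5, 10 and 15 patients

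*SAP*

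**What the plan says.** SAP section 12, Cohort 2, Toxicity Monitoring, states the rule five times:

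- **Formula:** "P(TOX, E) > 0.30 | \text{data}) > 0.85", with a Beta(0.6, 1.4) prior on the toxicity rate.
- **Words:** the following sentence, offered as a restatement of the formula, requires "more than 90% chance that the toxicity is more than 30" per cent.
- **Worked example:** accrual stops with 3 toxicities among the first 5 patients.
- **Table 9:** looks at 5, 10, 15 and 20 patients, with stopping counts of 3, 5, 7 and 9.
- **Table 10:** early stopping probabilities of 0.0089, 0.0787, 0.2607, 0.5173 and 0.7846 at true toxicity rates of 0.10 to 0.50, with average numbers treated of 20, 19, 17, 14 and 10.

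On timing, the text reads "We will apply the toxicity monitoring rule in cohort size of 5, starting from the 1st patient". Cohort 3 repeats all of this, with Tables 13 and 14 in place of Tables 9 and 10. Nothing in the section reconciles 0.85 with 90%.

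**The concern.** The sentence claims to say what the formula says, but its threshold is higher. A higher posterior threshold can require more toxicities before accrual stops, so the question is whether 0.85 and 0.90 give the same whole-number boundaries. If they did, the mismatch would be cosmetic. If not, the safety rule for two cohorts would give opposite instructions on the same data, and Tables 10 and 14 would describe only one of the two rules. The 90% reading would not look odd to someone comparing cohorts: it gives 4, 6 and 8 at 5, 10 and 15 patients, which are the Cohort 1 boundaries in Table 4.

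**Working it through.** **Inputs (SAP section 12, Cohort 2; identical for Cohort 3).** Prior Beta(0.6, 1.4); toxicity limit 0.30; looks at 5, 10, 15 and 20; maximum 20 patients; thresholds 0.85 (formula) and 0.90 (words).

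**Step 1: posterior at each count.** With x toxicities in n patients the posterior is Beta(0.6 + x, 1.4 + n − x). At 3/5, for example, it is Beta(3.6, 3.4). The probability above 0.30 is:

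| n | one below the printed boundary | printed boundary | one above |
|---|---|---|---|
| 5 | 2: 0.6261 | 3: 0.8745 | 4: 0.9751 |
| 10 | 4: 0.7110 | 5: 0.8798 | 6: 0.9625 |
| 15 | 6: 0.7662 | 7: 0.8927 | 8: 0.9597 |
| 20 | 8: 0.8067 | 9: 0.9059 | 10: 0.9608 |

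The boundary is the smallest x whose posterior exceeds the threshold.

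- Threshold 0.85 gives 3, 5, 7, 9, which is Table 9 exactly.
- Threshold 0.90 gives 4, 6, 8, 9.

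The rules differ by one patient at 5, 10 and 15, and agree at 20.

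**Step 2: reproduce Table 10.** Toxicities in each group of 5 are binomial with the true rate. Carry forward the paths that have not stopped and add up the stopping probability at looks 5, 10 and 15; reaching a boundary at the maximum of 20 is not an early stop. For the average number treated, weight 5, 10 and 15 by the probability of stopping there and 20 by the remainder.

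At a true rate of 0.50:

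- Boundaries 3/5/7: 0.5000 + 0.1865 + 0.0972 = 0.7837. Average = 5 × 0.5000 + 10 × 0.1865 + 15 × 0.0972 + 20 × 0.2163 = 10.1.
- Boundaries 4/6/8: 0.1875 + 0.2197 + 0.1516 = 0.5588. Average = 5 × 0.1875 + 10 × 0.2197 + 15 × 0.1516 + 20 × 0.4412 = 14.2.

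| True rate | Table 10: stop early (avg N) | 0.85 rule | 0.90 rule |
|---|---|---|---|
| 0.10 | 0.0089 (20) | 0.0094 (19.9) | 0.0006 (20.0) |
| 0.20 | 0.0787 (19) | 0.0777 (19.0) | 0.0132 (19.8) |
| 0.30 | 0.2607 (17) | 0.2571 (16.8) | 0.0844 (19.1) |
| 0.40 | 0.5173 (14) | 0.5277 (13.5) | 0.2736 (17.2) |
| 0.50 | 0.7846 (10) | 0.7837 (10.1) | 0.5588 (14.2) |

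The 0.85 rule matches Table 10 closely. The largest gap is 0.5277 − 0.5173 = 0.0104, at a true rate of 0.40. The SAP does not say how Table 10 was produced. If it was simulated, one standard error at that point is √(0.5277 × 0.4723 / 1,000) = 0.016 for an assumed 1,000 runs, or 0.005 for 10,000. The 0.90 rule misses the same entry by 0.5173 − 0.2736 = 0.2437.

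**Step 3: sensitivity to the looks.** If reaching the boundary at 20 also counts as stopping, 0.85 against 0.90 gives 0.8425 against 0.7702 at a true rate of 0.50, and 0.5795 against 0.4416 at 0.40. The gap narrows but remains. The text also speaks of stopping at any time. Looks after every patient do not reproduce Table 10 as a whole under either threshold. The nearest 0.90 variant at high toxicity rates, with looks from patient 5 to patient 19, gives 0.7939 at a true rate of 0.50 but 0.2154 at 0.30 and 0.0032 at 0.10, against 0.2607 and 0.0089 printed.

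**The case against.** Four of the five statements in each cohort agree: the formula, the boundary table, the worked example and the operating characteristics. The formula is introduced as the rule itself, and the 90% sentence is only a paraphrase. In practice staff will read an integer from Table 9 or 13 rather than compute a beta posterior, and will stop at 3/5. On that reading Tables 10 and 14 overstate nothing, no arithmetic is wrong, and the printed boundaries are the more cautious of the two.

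Most of this stands. The loss of protection is conditional on the sentence being followed, and the defect is a contradiction in wording rather than a miscalculation. But the SAP does not say that the table takes precedence. It says that the boundaries rest on the stated monitoring conditions, and those conditions are stated in two ways. Anyone who programs the rule from the prose, or checks the table against it, would conclude that three of the four boundaries are wrong. The worked example itself, with a posterior of 0.8745, fails the sentence it is meant to illustrate.

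**Conclusion.** The contradiction is real and appears in both cohorts. The formula and tables stop accrual at 3/5, 5/10 and 7/15; the sentence does not. If the sentence were applied, early stopping would fall by 22.5 percentage points at a true toxicity rate of 50% (78.4 − 55.9), by 25.4 at 40% (52.8 − 27.4) and by 17.3 at 30% (25.7 − 8.4). At 50%, about four more patients would be treated on average (14.2 − 10.1 = 4.1). These figures assume the stated prior, looks at 5, 10 and 15, and a maximum of 20 patients per cohort. Because this is a safety stopping rule and one patient separates the two readings at every look before the last, it must be corrected. The SAP does not show which threshold was intended, and this review takes no position on that.

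**What to change.** In the Toxicity Monitoring text of both cohorts, make the formula, sentence, worked example, boundary table and operating characteristics state one threshold. The sponsor decides which.

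- **If the formula and tables stand:** change one number in each of two sentences. Nothing needs recomputing.
- **If the 90% sentence stands:** change both formulas and both worked examples, and recompute Tables 9, 10, 13 and 14. This is a short calculation, but the stated protection falls to the 0.90 column above and should be reviewed as such.

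In the same edit, state that the rule is applied only at the tabulated looks, if that is the intention, so that the wording about stopping at any time does not conflict with looks every 5 patients.

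### The Cohort 3 futility example sets the cut-off at 0 of 10 responders, while the stated rule, Table 11 and Table 12 all use 0 or 1 of 10; the Cohort 2 example is true but incomplete

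*SAP*

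**What the plan says.** All references are to SAP section 12, Futility Monitoring, under Cohort 2 and Cohort 3. The two cohorts share one design:

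- The historical ORR is 20% and the target is 35%.
- Enrolment stops when there is a "less than 2.5% chance that ORR rate of the IMGN901 is greater than the ORR rate of standard treatment by 15" percentage points, which means when Pr(ORR > 0.35 | data) < 0.025.
- The prior for the ORR is Beta(0.4, 1.6).
- The boundaries are applied in groups of 10 patients and tabulated at 10 and 20.

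Tables 7 and 11 label the boundary row as less than or equal to, and give 0-1 at 10 patients. Tables 8 and 12 are identical, with an early-stopping probability of 0.3758 and an average of 16 patients at a true ORR of 20%.

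The worked examples read differently. Cohort 3: "accrual will cease if less than 1 patients experiences overall response among the first 10 patients treated". Cohort 2: "accrual will cease if 0 patients experiences overall response among the first 10 patients treated".

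**The concern.** In Cohort 3 the example is worded as a threshold. Fewer than 1 means 0, so a cohort with exactly 1 responder in 10 would continue under the sentence and stop under Table 11. The Cohort 2 sentence does not contradict Table 7, but it gives only half of the stopping region and could be taken for the whole of it.

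The look at 10 patients is the only tabulated futility look before 20, so it is the only one that can shorten a cohort for lack of response. The SAP does not say whether text or table prevails if they differ. A stopping rule should have a single reading before data arrive. Otherwise the reading can be chosen after 1 of 10 has been observed, and Table 12 would not describe the trial if the example were chosen.

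**Working it through.** **Inputs (SAP section 12, Cohorts 2 and 3).** Prior Beta(0.4, 1.6); threshold 0.20 + 0.15 = 0.35; stop if the posterior probability is below 0.025; look at n = 10. A maximum of 20 patients is assumed, being the last tabulated size and the value that the average-size columns approach.

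**Step 1: the boundary implied by the rule.** With x responders in 10, the posterior is Beta(0.4 + x, 11.6 − x).

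| x of 10 | Pr(ORR > 0.35 given data) | Below 0.025? |
|---|---|---|
| 0 | 0.0012 | yes, stop |
| 1 | 0.0215 | yes, stop |
| 2 | 0.1043 | no, continue |

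The rule stops at 0 or 1, as Tables 7 and 11 print.

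**Step 2: reproduce the plan's operating characteristics.** For a cut-off at 1 or fewer, P(stop) = (1 − p)^10 + 10p(1 − p)^9. At p = 0.20 this is 0.1074 + 0.2684 = 0.3758. Average size is 20 − 10 × P(stop) = 20 − 3.758 = 16.2, printed as 16.

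**Step 3: compare with the example's cut-off.** For a cut-off at 0 only, P(stop) = (1 − p)^10.

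| True ORR | Tables 8 and 12 | P(X ≤ 1) | P(X = 0) |
|---|---|---|---|
| 0.20 | 0.3758 | 0.3758 | 0.1074 |
| 0.25 | 0.2440 | 0.2440 | 0.0563 |
| 0.30 | 0.1493 | 0.1493 | 0.0282 |
| 0.35 | 0.0860 | 0.0860 | 0.0135 |
| 0.40 | 0.0464 | 0.0464 | 0.0060 |
| 0.45 | 0.0233 | 0.0233 | 0.0025 |

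All six tabulated values match the cut-off at 1 or fewer to four decimals, and none matches the cut-off at 0.

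**Step 4: size at a true ORR of 20%.**
- Early stopping is 0.107 under the example and 0.376 under the tables. The difference, 0.2684, is the probability of exactly 1 of 10.
- Average size under the example is 20 − 1.074 = 18.9, against 16.2, a difference of 2.7 patients.
- Cohorts passing the look: 1 − 0.3758 = 62% under the intended boundary and 1 − 0.1074 = 89% under the example.

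**The case against.** The strongest reply is that nothing at 10 patients is miscalculated. The SAP refers the reader to Tables 7 and 11 for the boundaries and says that those boundaries will be applied. The sentences at issue open as examples, and 0 of 10 does stop. Response and toxicity summaries go to the IND Medical Monitor under section 12, which contains the rule and the tables.

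Much of this stands. It disposes of any claim that Cohort 2 contradicts itself: its sentence is a correct illustration and does not say that 1 of 10 continues. It does not rescue Cohort 3, where the wording is a cut-off that excludes 1. The toxicity examples in the same section also quote the boundary value itself (4 or more of 5 in Cohort 1, matching Table 4; 3 of 5 in Cohorts 2 and 3, matching Tables 9 and 13). A reader therefore has some reason to take the response example in the same way.

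Two stronger readings are tempting. A reader might infer that the futility look is largely disabled in both cohorts. The documents do not support that, because nothing in the SAP makes the example override the table below it. A reader might also infer that the example is what sends most inactive cohorts on to 20 patients. At a true ORR of 20%, 62% pass the look under the intended boundary anyway; the example would raise this to 89%.

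**Conclusion.** The inconsistency is real and can be resolved from the SAP alone. At 10 patients the posterior rule, the boundary tables and the operating characteristics agree on 0 or 1 responders. The Cohort 3 example contradicts them, and the Cohort 2 example is incomplete.

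The cost is conditional on the example being followed rather than the table. In that case early stopping would fall from 0.376 to 0.107 at a true ORR of 20%, from 0.244 to 0.056 at 25%, and from 0.086 to 0.013 at the 35% target. These figures assume one futility look at 10, a maximum of 20 patients and no stopping for toxicity, which is the basis that reproduces Tables 8 and 12.

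Severity is moderate: an inconsistent stopping rule that should be corrected, but not a defect in the design or its calculations.

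Two neighbouring matters are separate and do not affect this result. At 20 patients the tables print 2-4, whereas the rule stops at 3 or fewer (posterior 0.0154 at 3 and 0.0516 at 4). The Cohort 3 futility formula also prints the toxicity symbol where the surrounding text shows that the ORR is meant.

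**What to change.** Reword the example in both cohorts so that accrual stops when 1 or fewer of the first 10 treated patients have an overall response. This matches the stated posterior rule, Tables 7 and 11 at 10 patients, and Tables 8 and 12. A short statement that the tabulated boundaries prevail over illustrative text would remove any remaining doubt.

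The cost is one sentence in each of two cohorts. The boundary at 10 patients, the operating characteristics and the sample size stay as they are.

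### Duration of response is listed for plain descriptive summary as well as Kaplan-Meier; the plain mean is biased low if any response is censored at cut-off

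*SAP*

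**What the plan says.** Both statements stand in one paragraph, under the Statistical Analysis Plan heading at the end of SAP section 12.

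- **Descriptive summary.** "Demographic/clinical characteristics (including duration of response) and safety data of the patients will be summarized using descriptive statistics such as mean, standard deviation". The full list of statistics is "descriptive statistics such as mean, standard deviation, median and range". Nothing is said about responses still ongoing, or about limiting the summary to responses that have ended.
- **Time-to-event analysis.** "The distribution of time-to-event endpoints including duration of response, overall survival and progression free survival will be estimated using the method of Kaplan and Meier". Subgroups follow the same approach: "Comparisons of time-to-event endpoints by important subgroups will be made using the log-rank tests".
- **Analysis set.** "All patients who received any dose of the study agent will be included in the analysis for efficacy and safety". The paragraph does not separately state that duration of response is summarised in responders only.

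The SAP does not say how the two summaries relate or which one is the reported result.

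**The concern.** Duration of response is an outcome that arises after treatment starts and exists only in responders. It can be incomplete at the data cut-off. By calling it a time-to-event endpoint, the SAP itself accepts that it may be censored. A mean, standard deviation, median and range have no means of handling a censored value. The analyst must either count the time observed so far as if the response had ended, or drop the patient. Either choice pulls the mean down, because the longest responses are the ones most likely to be unfinished.

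At stake is the description of a secondary outcome. A programmer who follows the first sentence literally produces a table that understates durability and can sit beside a Kaplan-Meier estimate that differs from it, with no rule for which is quoted. Responder numbers are small. The monitoring tables run to 20 patients per cohort. At the historical and target rates this is 20 × 0.30 = 6 to 20 × 0.50 = 10 responders in cohort 1, and 20 × 0.20 = 4 to 20 × 0.35 = 7 in cohorts 2 and 3. One or two unfinished responses can therefore move a plain mean noticeably.

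**Working it through.** **Figures in the plan.** The SAP states no figure for duration of response, so there is nothing to reproduce. The conflict is textual: one sentence assigns the endpoint to methods without censoring, another to methods with it. The arithmetic below shows only the direction of the bias and how it depends on censoring.

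**Assumptions, none from the SAP.** Duration T is exponential with rate λ = ln 2 / median. Follow-up after response, C, is independent of T. The recorded time is X = min(T, C).

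**General result.** For exponential T, E[X] = P(T ≤ C) / λ = (1 − c) × true mean, where c is the proportion censored. The plain mean therefore falls short by exactly the censored fraction, and the shortfall is zero when c = 0.

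**Case A: random (exponential) censoring, true median 6 months.** λ = 0.693 / 6 = 0.1155, so the true mean is 1 / 0.1155 = 8.66. The plain median is (1 − c) × 6.0.

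| Censored | Plain mean (true 8.66) | Plain median (true 6.0) |
|---|---|---|
| 0% | 8.66 | 6.0 |
| 10% | 7.8 | 5.4 |
| 20% | 6.9 | 4.8 |
| 30% | 6.1 | 4.2 |
| 40% | 5.2 | 3.6 |
| 50% | 4.3 | 3.0 |

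In this case, dropping the censored patients gives the same values as counting their times as complete. In simulation of the same scenarios, the Kaplan-Meier median stayed between 5.9 and 6.0 throughout.

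**Case B: staggered follow-up, C uniform on 3 to 18 months.** The censored proportion is c = (e^(−3λ) − e^(−18λ)) / (15λ).

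- True median 6: c = (0.7071 − 0.1250) / 1.733 = 0.336. Plain mean = 0.664 × 8.66 = 5.75 against 8.66. The plain median solves e^(−λt) × (18 − t)/15 = 0.5, giving t = 4.9 against 6.0.
- True median 12: λ = 0.0578 and the true mean is 17.3. c = (0.8409 − 0.3536) / 0.8664 = 0.562. Plain mean = 0.438 × 17.3 = 7.6 against 17.3. The plain median is 6.9 against 12.
- Using completed responses only is worse: means 4.4 and 5.2, medians 3.5 and 4.3, for the two scenarios in turn.

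**Case C: one common follow-up F for every responder, true median 6 months.** Plain mean = (1 − e^(−λF)) / λ.

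| F (months) | Censored | Plain mean (true 8.66) | Plain median, censored times kept | Completed responses only: mean / median |
|---|---|---|---|---|
| 6 | 50% | 4.3 | 6.0 | 2.7 / 2.5 |
| 12 | 25% | 6.5 | 6.0 | 4.7 / 4.1 |
| 18 | 12.5% | 7.6 | 6.0 | 6.1 / 5.0 |
| 24 | 6% | 8.1 | 6.0 | 7.1 / 5.5 |

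**Reading the cases together.** The mean is low in every case with any censoring. The plain median is low under random or staggered follow-up (A and B). It is unaffected when all responders share a follow-up at least as long as the true median and censored times are kept (C).

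**The case against.** The strongest reply is that the right method is already in the plan. Only the later sentence calls duration of response an endpoint and says how its distribution is estimated, and a descriptive listing can sit beside a Kaplan-Meier curve. This stands in part: the planned Kaplan-Meier result is sound, which keeps the point small. It does not remove the first sentence, which names the variable explicitly and assigns it statistics that are wrong once a response is censored.

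A second reply is that the parenthesis could mean the duration of a previous response, a completed baseline quantity, since cohort 1 has failed prior therapy. The SAP does not exclude this in so many words. The reading is strained, because the same term reappears a few sentences later as an on-study endpoint with no distinction drawn.

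Three stronger readings are tempting, and the document does not support them.

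- **That the SAP will report two different medians.** The list is introduced as examples for a mixed group of demographic, clinical and safety variables. It permits a plain median of duration of response but does not guarantee one.
- **That the descriptive figure is biased in any event.** The bias is conditional on censoring, and the median can escape it (Case C).
- **That a decision on the drug turns on it.** For cohort 1 the SAP ties further investigation to ORR with acceptable toxicity. The stopping rules in all three cohorts use response and toxicity counts, and none uses duration of response.

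It is also fair to say that the magnitudes rest on assumed inputs. The 56%-censored scenario is the most extreme shown, and nothing in the SAP makes it more likely than the milder ones.

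**Conclusion.** The point holds as a minor inconsistency with a conditional statistical consequence. One paragraph assigns duration of response both to plain descriptive statistics and to Kaplan-Meier. If any response is ongoing or lost to follow-up at cut-off, the plain mean is biased low; under staggered follow-up the plain median is too. If every response has ended by cut-off, there is no bias.

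The size cannot be derived from the SAP. Under the exponential assumption the mean is low by the censored fraction, so 10% to 50% censoring means a mean 10% to 50% too low. Other duration distributions would give other amounts.

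The primary ORR estimate and its interval, the response and toxicity boundaries, and the planned Kaplan-Meier and log-rank analyses are untouched. This is worth correcting because it is easy to do, not because it threatens the trial's conclusions.

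**What to change.** Delete the parenthesis naming duration of response from the descriptive-statistics sentence. State that duration of response is reported in responders by Kaplan-Meier: median with 95% CI and number censored. The observed range may still be listed, provided censored values are marked.

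The cost is one deleted phrase and one clarified sentence, with no new analysis. The small downside is that with roughly 4 to 10 responders per cohort the Kaplan-Meier median may not be reached. The marked range and the number censored then still describe what was seen.
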